9.3.2 Pharmacokinetic Statistical Methodology

All tests of treatment effects will be conducted at a 2-sided alpha level of 0.1, unless otherwise stated, and all CIs will be given at a 2-sided 90% level.

The primary parameters for analysis will be AUC(0- ∞) of LY3819253 following SC administration. Other noncompartmental parameters, such as half-life, t_{max} , apparent clearance, and volume of distribution following SC administration may be reported.

The natural log (ln)-transformed AUC(0- ∞) will be analyzed using an analysis of variance model. The model will include dose as a factor. Body weight may be tested as a covariate and kept if needed.

The least squares mean for each treatment, difference in least square means between the treatments, and corresponding 90% CI will be calculated; these values will then be back-transformed to give the geometric least square mean, ratio of geometric least square means, and corresponding 90% CI.

Example SAS code for the analysis:

```
proc mixed data=pk;
  class dose;
  model log_pk = dose / alpha=0.1 cl residual ddfm=kr2;
  lsmeans dose / cl pdiff;
  ods output lsmeans=lsm;
  ods output diffs=diff;
  ods output tests3=tests;
run;
```

In addition to noncompartmental analysis, the data may be combined with data from other studies to be analyzed using non-linear mixed-effect modelling of the PK data. This analysis will be the responsibility of Eli Lilly PK/PD group.

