6.1. Study Interventions Administered

Intervention	LY3819253	Placebo
Type	Biologic	Not applicable
Dose Formulation	solution	0.9% sodium chloride solution
Unit Dose Strength(s)	262.5 mg/2.1 mL vial (125 mg/mL)	Placebo
Planned Dosage Level(s)	Cohort 1: 350 mg Cohort 2: 700 mg Cohort 3: 700 mg	Not applicable
Route of Administration	SC injection	SC injection
Use	experimental	placebo
IMP and NIMP	IMP	IMP
Sourcing	From Lilly	Commercially available 0.9% sodium chloride solution
Packaging and Labeling	Study Intervention will be provided in glass vials and will be labeled appropriately	Commercially available 0.9% sodium chloride solution will be used as a placebo for this study

Abbreviations: IMP = investigational medicinal product; NIMP = non-investigational medicinal product;
SC = subcutaneous.

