6.1.1. Injection volumes and formulation concentrations

Injection volumes are as follows:

Cohort (LY3819253 dose)	Number of injections and volumes
Cohort 1 (350 mg)	2x 1.4 mL
Cohort 2 (700 mg)	1x 1.4 mL + 2x 2.1 mL
Optional Cohort 3 (700 mg)	2x 1.9 mL + 1x 1.8 mL*

* Doses may be adjusted based on data review during the study, as described in Section 6.6. In this event, the number or volume of injections, or both, will be adjusted accordingly.

The LY3819253 formulation concentration will be 125 mg/mL in all cases.

6.1.2. In the Event of a Retrospective Positive Sterility Finding from Prepared Study Intervention

If a positive sterility finding occurs in the terminally sterile filtered study intervention, the participants who were dosed from the impacted batch should be contacted immediately and undergo a full physical examination including, but not limited to, blood pressure, pulse rate, and body temperature.

A blood sample should be collected for culture and assayed for inflammatory markers such as C-reactive protein and elevations in white blood cell counts.

If the signs and symptoms indicated a participant has a possible infection, they will be clinically managed, treated, and followed up until resolution. Any AEs will be recorded as appropriate.

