5.3 Inpatient Stay

Participants will be admitted to the study site on Day -1. They will remain inpatient until discharge on Day 7 after study procedures are complete.

Dosing

Dosing will occur on Day 1. Intended doses of LY3819253 are as follows:

- Cohort 1: 350 mg
- Cohort 2: 700 mg
- Cohort 3 (optional): 700 mg (alternative injection volumes)

Participants will undergo PK sampling and safety assessment after dosing.

For Cohorts 1 and 2, a safety review will be conducted to determine whether it is appropriate to proceed with dosing of the next cohort. This safety review will be conducted based on data from at least 4 participants, after at least 4 days after dosing.

Sentinel dosing

Cohort 1 will include sentinel dosing. The first 2 participants will be randomized and dosed (1 LY3819253: 1 placebo).

The investigator and the Lilly sponsor team are responsible for determining if safety and tolerability is acceptable to continue with dosing subsequent participants.

Tolerability as measured by ISRs and their severity is anticipated to be the main safety consideration for this assessment. While no serious systemic reactions have been seen with LY3819253 to date, participants will be closely monitored.

If the investigator and Lilly sponsor team determine that safety and tolerability is acceptable, the remaining participants in the cohort will be dosed on the next day.

Cohort 2 and the optional Cohort 3 will not include sentinel dosing.

Postdose sampling

On Days 1 through 7, participants will undergo PK sampling and safety assessment.

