6. TREATMENTS

The following is a list of the study treatment abbreviations that will be used in the TFLs.

Cohort	Study Treatment Name*	Treatment order in TFL
All	Placebo SC	1
1	350 mg LY3819253 SC (2x 1.4 mL)	2
2	700 mg LY3819253 SC (1x 1.4 mL + 2x 2.1 mL)	3
3 (optional)	700 mg LY3819253 SC (1x1.8 mL + 2x 1.9 mL)	4

*The LY3819253 formulation concentration will be 125 mg/mL in all cases.

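### Does naming dose as the only factor in the AUC(0-∞) model merge the two 700 mg regimens?

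*SAP*

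**What the plan says.** SAP 9.3.2 sets out the only model for the primary endpoint. Its factor sentence reads "The model will include dose as a factor", and body weight is an optional covariate. The next paragraph gives the deliverable: "The least squares mean for each treatment, difference in least square means between the treatments, and corresponding 90% CI will be calculated". The block headed as example SAS code uses `dose` in CLASS and MODEL, and again in "lsmeans dose / cl pdiff". No cohort or treatment variable appears, and the levels of `dose` are not listed.

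SAP Section 6 says what a treatment is: "The following is a list of the study treatment abbreviations that will be used in the TFLs". It has four rows: placebo, 350 mg (Cohort 1), 700 mg as 1 × 1.4 mL + 2 × 2.1 mL (Cohort 2), and for Cohort 3 "700 mg LY3819253 SC (1x1.8 mL + 2x 1.9 mL"). The two 700 mg rows have separate names and separate table order numbers (3 and 4). SAP 5.3 also sets the last one apart: "Cohort 3 (optional): 700 mg (alternative injection volumes").

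The protocol's dose lists are in milligrams. Section 6.1 has "Cohort 1: 350 mg Cohort 2: 700 mg Cohort 3: 700 mg", and the table in Section 6.1.1 heads its first column "Cohort (LY3819253 dose").

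**The concern.** Taken literally in milligrams, `dose` cannot deliver what the following paragraph promises once Cohort 3 is enrolled at 700 mg. The procedure would run without an error message and put both 700 mg regimens in one level. The primary model would then give no separate mean or 90% interval for Cohort 2 or Cohort 3 and no ratio between them, although injection volume is the only stated difference between those cohorts. SAP Section 7 also states its precision per cohort. If the coding were really open, it could be settled after the results were known.

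**Working it through.** **1. Do two treatments share a dose?** Volumes come from Protocol 6.1.1 and SAP Section 6; the concentration is 125 mg/mL.

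- Cohort 1: 2 × 1.4 = 2.8 mL; 2.8 × 125 = 350 mg
- Cohort 2: 1.4 + 2 × 2.1 = 5.6 mL; 5.6 × 125 = 700 mg
- Cohort 3: 1.8 + 2 × 1.9 = 5.6 mL; 5.6 × 125 = 700 mg

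They do. The PK population (SAP Section 8) contains LY3819253 recipients only, so placebo adds no level.

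**2. What each coding produces with three cohorts**

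| Coding of the factor | Levels | LS means | Ratios |
|---|---|---|---|
| Milligrams | 2 | 2 | 1 |
| Section 6 treatment | 3 | 3 | 3 |

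With Cohorts 1 and 2 only, the two codings are identical.

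**3. The plan's own precision figure.** SAP Section 7 gives about a 70% chance that the 90% interval lies within (0.7, 1.43) of the geometric mean, with n = 6 and CV 40%. The check is P(t × s/√n ≤ ln(1/0.7)), with t the 0.95 quantile on 5 df and 5s²/σ² chi-square on 5 df.

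- σ = 0.40: 68.1%
- σ = √ln(1 + 0.4²) = 0.3853: 72.5%

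Both round to the stated figure. They use the cohort's own 5 df. With a variance pooled over three cohorts of 6 (15 df, σ = 0.3853) the chance would be 95.1%. The Section 7 statement therefore matches an interval computed within one cohort, not one from the ANOVA.

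**4. Interval widths**, with σ = 0.3853 and factor exp(t × σ × √v).

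- One cohort mean, treatment coding, 6/6/6: exp(1.753 × 0.3853 × √(1/6)) = 1.32 (15 df)
- Pooled 700 mg mean, milligram coding, 6/6/6: exp(1.746 × 0.3853 × √(1/12)) = 1.21 (16 df)
- Cohort 3/Cohort 2, 7 vs 7 (7/7/7): exp(1.734 × 0.3853 × √(2/7)) = 1.43 (18 df)
- Cohort 3/Cohort 2, 7 vs 5 (7/7/5): exp(1.746 × 0.3853 × √(1/5 + 1/7)) = 1.48 (16 df)
- 700/350 at 7/7/7: pooled exp(1.729 × 0.3853 × √(1/7 + 1/14)) = 1.36 (19 df); a single 700 mg cohort 1.43 (18 df)

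**5. Effect of pooling on the residual.** The documents give no Cohort 3/Cohort 2 ratio. If it were 0.80 (an assumption), the expected residual SD at 7/7/7 would be √(0.3853² + 3.5 × ln(0.8)²/19) = 0.397 against 0.385.

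**6. What survives under the milligram coding.** SAP 9.1 gives N, geometric mean and geometric CV for the AUCs, and Section 6 sets the treatment names for the tables. From those figures a cohort's own interval can be recovered: at n = 6 and 40% CV it is exp(2.015 × 0.3853/√6) = 1.37 on 5 df.

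**7. Which reading the SAP supports.** The factor sentence and code say dose; the output sentence says treatment, and Section 6 lists the treatments. Only treatment coding satisfies both. The sponsor also uses the word loosely for the group: the protocol synopsis speaks of up to three dose cohorts, and SAP 9.4.7 puts a per-dose count beside a by-treatment summary.

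**The case for a change.** The best case for a change is that this is the only model for the only primary endpoint, and its code says `dose`. A programmer with a numeric milligram variable would pool two regimens without a warning. The milligram sense is natural, because the protocol's dose lists use it. Naming the treatment instead would cost one residual degree of freedom (19 to 18 at 7/7/7) and close off a later choice.

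Part of this stands. The wording is loose, SAP 9.3.2 never lists the levels, and Protocol 9.4.2 specifies no ANOVA that could settle them. The TFL shells mentioned in SAP Section 3 may do so, but they are not among the documents and cannot be relied on here.

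The rest carries less weight. The slip would show: two means cannot fill rows for three active treatments that Section 6 names and orders. The Section 7 precision statement does not depend on the ANOVA (step 3), and its target of 18 evaluable participants is weak support, since Protocol 9.2 sets a minimum for Cohorts 1 and 2 only. Protocol 9.1 plans no formal testing, so no error rate is at stake, and no listed objective asks for a Cohort 3/Cohort 2 contrast. That ratio would in any case be known only to within ×/÷ 1.43 to 1.48.

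**Conclusion.** No change is needed. The SAP leaves the levels of a factor unstated, but its output sentence and its treatment list point to one level per treatment, and the code is labelled an example. The alternative reading needs three things together: Cohort 3 is enrolled, its dose equals another cohort's (Protocol 1.2 and 6.1.1 allow it to change), and the analyst codes in milligrams against the stated deliverable. The result would then be one pooled 700 mg mean at ×/÷ 1.21 in place of two at ×/÷ 1.32, which is still a valid descriptive summary by milligram dose. Each regimen's geometric mean and CV would remain available in by-treatment summaries. The widths assume 40% CV and 6 evaluable per cohort. Any bias from pooling depends on a Cohort 3/Cohort 2 ratio that the documents do not give, so none is claimed.

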9.4. Statistical Analyses

Statistical analysis of this study will be the responsibility of sponsor or its designee.

All tests of treatment effects will be conducted at a 2-sided alpha level of 0.1, unless otherwise stated, and all confidence intervals will be given at a 2-sided 90% level.

Any change to the data analysis methods described in the protocol will require an amendment only if it changes a principal feature of the protocol. Any other change to the data analysis methods described in the protocol, and the justification for making the change, will be described in the SAP and the clinical study report. Additional exploratory analyses of the data will be conducted as deemed appropriate.

The SAP will be finalized prior to unblinding and it will include a more technical and detailed description of the statistical analyses described in this section. This section is a summary of the planned statistical analyses of the most important endpoints including primary and key secondary endpoints.

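### The example PROC MIXED code in SAP 9.3.2 would give 95% limits, not the required 90% limits, because LSMEANS carries no alpha= option

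*SAP*

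**What the plan says.** Protocol Section 9.4 sets the level for the whole study: "all confidence intervals will be given at a 2-sided 90% level". SAP Section 9.3.2 repeats it: "all CIs will be given at a 2-sided 90% level". The same SAP section then says which quantities carry these limits. They are computed for the least squares mean of each treatment and for the differences between treatments, and "these values will then be back-transformed to give the geometric least square mean, ratio of geometric least square means, and corresponding 90% CI".

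Below that, under the label "Example SAS code for the analysis", the SAP gives one PROC MIXED step. Its MODEL statement is "model log_pk = dose / alpha=0.1 cl residual ddfm=kr2". Its LSMEANS statement is "lsmeans dose / cl pdiff". The results are saved with "ods output lsmeans=lsm" and "ods output diffs=diff", plus a dataset of type 3 tests. No other line of the code sets a confidence level.

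**The concern.** The 90% level is written on one statement, and the limits that will be reported come from another. In PROC MIXED, `alpha=` on MODEL governs the limits for the fixed-effect parameter estimates. Limits for least squares means and their differences follow the `alpha=` on LSMEANS, which is 0.05 if omitted. The table that the MODEL option acts on is not among the saved datasets, so the `alpha=0.1` in the code affects none of the limits the SAP wants to report.

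AUC(0-∞) is the only primary endpoint, and this is the only statistical model specified for it. If the code is run unedited, the primary table would show 95% limits labelled as 90%. The slip is easy to miss, because `alpha=0.1` is visible in the code and neither the point estimates nor the p-values look different. The limits would also no longer be comparable with the precision statement in SAP Section 7, which is expressed for a 90% interval.

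**Working it through.** **Inputs.** Between-subject CV 40%, 6 evaluable active participants per cohort, and precision limits (0.7, 1.43) come from Protocol Section 9.2 and SAP Section 7. Allocation of 7 active to 2 placebo per cohort comes from Protocol Section 4.1.1. The 90% level comes from Protocol Section 9.4 and SAP Section 9.3.2. The LSMEANS default of 0.05 is a property of SAS, not a statement in the documents.

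**Step 1: reproduce the plan's own figure.** The plan gives about a 70% chance that the 90% interval lies within (0.7, 1.43) of the geometric mean with n = 6. For a single-cohort t interval on the log scale, the chance that the half-width is below w = ln(1/0.7) = 0.3567 is

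P = P(χ²_df ≤ df × [w√n / (t × σ)]²), with df = n − 1 = 5 and t = 2.015.

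- σ = √ln(1 + 0.4²) = 0.3853: 5 × [0.3567 × 2.449 / (2.015 × 0.3853)]² = 6.33, so P = 0.725.
- σ = 0.40 (CV taken directly as the log-scale SD): P = 0.681.

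The two readings bracket 70%, so the figure reproduces on this basis and depends on the 90% level. With 95% limits (t = 2.571) the same calculation gives 0.435 and 0.393. At n = 7 (df 6, t = 1.943 or 2.447) the chance is 82–85% at the 90% level and 53–58% at the 95% level.

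**Step 2: limits from the model as coded.** The example model pools the variance over doses. With two active cohorts of n each, df = 2n − 2. The limits are the estimate multiplied and divided by

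- geometric LS mean: exp(t × σ / √n)
- ratio of two LS means: exp(t × σ × √(2/n))

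With σ = 0.3853:

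| n per cohort (df) | t, 90% / 95% | Log-scale width, 95% ÷ 90% | LS mean factor, 90% / 95% | Ratio factor, 90% / 95% |
|---|---|---|---|---|
| 7 (12) | 1.782 / 2.179 | 1.22 | 1.30 / 1.37 | 1.44 / 1.57 |
| 6 (10) | 1.812 / 2.228 | 1.23 | 1.33 / 1.42 | 1.50 / 1.64 |

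**Step 3: an example.** Suppose the observed 700/350 mg ratio is 2.0.

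- n = 7 per cohort: 2.0 ÷ 1.443 and 2.0 × 1.443 give 1.39 to 2.89 at 90%. With 1.566 the limits are 1.28 to 3.13 at 95%.
- n = 6 per cohort: 2.0 ÷ 1.497 and 2.0 × 1.497 give 1.34 to 2.99 at 90%. With 1.641 the limits are 1.22 to 3.28 at 95%.

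**Step 4: sensitivity to the CV.** For the ratio with n = 6 per cohort, the factor is 1.46 instead of 1.36 at CV 30%, and 1.84 instead of 1.64 at CV 50%.

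**Step 5: the precision target on the pooled basis.** The Step 1 probabilities use one cohort at a time, as the plan's figure does. With the pooled variance of the coded model (n = 6 per cohort, df 10), the chance that the LS mean limits fall within (0.7, 1.43) is 85–89% at the 90% level and 53–59% (0.525 to 0.590) at the 95% level.

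**The case against.** The strongest reply is that the plan itself is not wrong. The SAP states the 90% level as a general rule, again for the LS means and differences, and again for the back-transformed ratios, and the protocol agrees. The code is labelled as an example, and SAP Section 3 describes the document as guidance. The fragment has no back-transformation step, so it must be extended before it can fill the reported table, and a programmer may see the level in the Alpha column of the output. Nothing depends on the limits either: Protocol Section 9.1 plans no formal hypothesis testing, Section 6.6.1 guides escalation by safety and tolerability, and the error makes the intervals wider.

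All of this stands and limits the severity. It does not make the code right. An example is there to show how the text is carried out, and this one gives a different confidence level. SAP Section 3 also says the SAP and table shells will serve as the template for the study report, so reuse of the code is plausible.

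A second reply is that the step from a missing option to 95% limits rests on how SAS behaves, which the documents do not state, and that the code was not run in SAS for this check. That is fair as a description of the evidence. The placement of the option can be read directly in the SAP, and the default can be confirmed by one run.

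A third reply is that the drop from 68–73% to 39–44% in the precision probability belongs to a single-cohort interval, not to the pooled model in the code. That is correct. The single-cohort figures show how far the plan's 70% depends on the level. The pooled figures in Step 5 describe the coded model.

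**Conclusion.** The code does not match the text. Run as printed, it would give 95% limits where both documents require 90% limits, for the LS means and ratios of the primary endpoint. The limits would be 22–23% too wide on the log scale for two cohorts of 7 or 6 active participants. Estimates and p-values are unaffected.

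The point is minor. It does harm only if the example is used without editing and the level goes unnoticed. The width figures assume the LSMEANS default of 0.05, equal numbers per cohort, no body-weight covariate and, apart from the stated sensitivity range, a CV of 40%. The sample size statement itself is not in question.

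**What to change.** Add `alpha=0.1` to the options of the LSMEANS statement, after `cl pdiff` and before the semicolon. The option has to be on LSMEANS; setting it on MODEL or on the PROC MIXED line should not be relied on. When the program is first run, confirm that the Alpha column of the saved LS means and differences datasets shows 0.1.

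The cost is one option on one line of example code. It needs no new data and changes no design feature, point estimate or p-value.

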9.4 Safety and Tolerability Assessments

9.4.1 Adverse events

Where changes in severity are recorded in the Case Report Form (CRF), each separate severity of the AE will be reported in the listings, only the most severe will be used in the summary tables. A pre-existing condition is defined as an AE that starts before the subject has provided written informed consent and is ongoing at consent. A non-treatment emergent AE is defined as an AE which starts after informed consent but prior to dosing. A TEAE is defined as an AE which occurs postdose or which is present prior to dosing and becomes more severe postdose.

All AEs will be listed. All TEAEs will be summarized by treatment, severity and relationship to the study drug. The frequency (the number of AEs, the number of subjects experiencing an AE and the percentage of subjects experiencing an AE) of TEAEs will be summarized by treatment, Medical Dictionary for Regulatory Activities (MedDRA) version 23.0 system organ class and preferred term. The summary and frequency AE tables will be presented for all causalities and those considered related to the study drug by the investigator. Any SAEs will be listed.

Discontinuations due to AEs will be listed.

9.4.2 Concomitant medication

Concomitant medication will be coded using the WHO drug dictionary (Version March 2020 B3). Concomitant medication will be listed.

9.4.3 Clinical laboratory parameters

All clinical chemistry and hematology data will be summarized by parameter and treatment, together with changes from baseline, and listed. Baseline is defined as the Day -1 predose assessment. Urinalysis data will be listed. Additionally, clinical chemistry, hematology and urinalysis data outside the reference ranges will be listed and flagged on individual subject data listings.

Data from SARS-CoV-2 clinical screening, serology, and point-of-care test will be listed, if available.

9.4.4 Vital signs

Vital signs data will be summarized by treatment together with changes from baseline, where baseline is defined as the Day 1 predose assessment. Figures of mean vital signs and mean changes from baseline profiles will be presented by treatment.

Values for individual subjects will be listed.

9.4.5 Electrocardiogram (ECG)

ECGs will be performed for safety monitoring purposes only and will not be presented. Any clinically significant findings from ECGs will be reported as an AE.

9.4.6 Immunogenicity Assessments

The frequency and percentage of subjects with pre-existing antidrug antibody (ADA) and with TE ADAs to LY3819253 will be tabulated and listed only if the data is available.

The frequency and percentage of subjects with cross-reactive and neutralizing antibodies, if measured, may also be tabulated for subjects with TE ADA.

9.4.7 Injection-Site Reactions

ISR data (including erythema, induration, pain, pruritus, and edema) will be listed and summarized by treatment in frequency tables. ISR will be listed and may be summarized if there are ≥ 3 subjects with ISR per dose.

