4.1.2. Inpatient stay

Participants will be admitted to the study site on Day -1. They will remain inpatient until discharge on Day 7 after study procedures are complete.

Dosing

Dosing will occur on Day 1. Intended doses of LY3819253 are as follows:

- Cohort 1: 350 mg
- Cohort 2: 700 mg
- Cohort 3 (optional): 700 mg (alternative injection volumes)

See Section 6.1 for detail of injection volumes.

Participants will undergo PK sampling and safety assessment after dosing.

For Cohorts 1 and 2, a safety review will be conducted to determine whether it is appropriate to proceed with dosing of the next cohort. This safety review will be conducted based on data from at least 4 participants, after at least 4 days after dosing.

Sentinel dosing

Cohort 1 will include sentinel dosing. The first 2 participants will be randomized and dosed (1 LY3819253:1 placebo).

The investigator and the Lilly sponsor team are responsible for determining if safety and tolerability is acceptable to continue with dosing subsequent participants.

Tolerability as measured by ISRs and their severity is anticipated to be the main safety consideration for this assessment. While no serious systemic reactions have been seen with LY3819253 to date, participants will be closely monitored.

If the investigator and Lilly sponsor team determine that safety and tolerability is acceptable, the remaining participants in the cohort will be dosed on the next day.

Cohort 2 and the optional Cohort 3 will not include sentinel dosing.

Postdose sampling

On Days 1 through 7, participants will undergo PK sampling and safety assessment as shown in the SoA (Section 1.3).

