8.2.5. Injection Site Reaction Assessment

Injection site assessments using the ISR CRF, VAS if required (see below), and an exploratory tool (Scarletred) will be performed at times specified in the SoA (Section 1.3).

Injection site pain assessments are part of the solicited and spontaneous ISR assessments. The baseline assessment, and all positive responses of pain from then on, will require an additional assessment using the Pain VAS.

As there are multiple injections for each dose, ISR assessments will be done for each injection. Manifestations of a local ISR may include erythema, induration, pain, pruritus, and edema. Injection site findings will be captured on the eCRF.

Injection site reactions, if recorded as a result of the prespecified (or solicited) assessment, will be recorded as AEs only if they qualify as SAEs.

If a spontaneous (or unsolicited) ISR is reported by a participant or investigator, the ISR CRF will be used to capture additional information about this reaction (for example, degree and area of erythema) at additional visits until resolution of the event.

The VAS is a well-validated tool (Williamson and Hoggart 2005) to assess injection site pain; it is presented as a 100-mm line anchored by verbal descriptors, usually "no pain" and "worst imaginable pain." The participant will be asked to rate any pain at the injection site on a scale of 0 to 100 on the line, as soon as possible following each injection.

In addition, the exploratory tool (Scarletred) will be used to acquire exploratory ISR data at each of the time points where the ISR data is being collected by administration of the ISR CRF. Failure to take this assessment at any of the indicated time points will not result in a protocol deviation.

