9.4.4. Exploratory Endpoint: Injection Site Reaction Assessments

Injection site reactions will be listed and may be summarized by dose if data warrant.

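### Dose is tied to the number of injections (2 v 3), so participant-level ISR incidence can rise with dose with no per-injection effect; SAP 9.4.7 should state its counting unit and add a per-injection table

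*SAP*

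**What the plan says.** **Injection schemes.** Protocol 6.1.1 and SAP 6 agree. Cohort 1 is "350 mg LY3819253 SC (2x 1.4 mL" each, so two injections. Cohort 2 is "700 mg LY3819253 SC (1x 1.4 mL + 2x 2.1 mL" each, and the optional Cohort 3 is "700 mg LY3819253 SC (1x1.8 mL + 2x 1.9 mL" each, so three injections in both. The concentration is 125 mg/mL throughout.

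**Placebo.** SAP 6 gives placebo a single row covering all cohorts. Neither document states how many placebo injections are given or at what volume.

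**Collection.** Protocol 8.2.5: "As there are multiple injections for each dose, ISR assessments will be done for each injection".

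**Summary.** SAP 9.4.7 says the ISR data "will be listed and summarized by treatment in frequency tables". Its next sentence makes a summary optional, depending on at least three subjects with an ISR *per dose*. Protocol 9.4.4 has: "Injection site reactions will be listed and may be summarized by dose if data warrant". SAP 3 states that the SAP takes precedence over the protocol's statistical section.

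**The concern.** Every participant at 700 mg has three sites at which a reaction can occur, against two at 350 mg. If the frequency table counts participants with at least one reaction, the 700 mg rows will tend to be higher even when each injection carries the same risk. A reader of the table would take that as a dose response.

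Pooled placebo does not repair this. If placebo recipients get the same scheme as their cohort, the single placebo row mixes two-injection and three-injection participants. It matches neither active scheme and sits between them.

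The threshold sentence adds a second problem. It is worded per dose, while the sentence before it works by treatment. Read literally, it could combine the two 700 mg cohorts, which differ only in how the volume is split. It also has no meaning for placebo, which has no dose.

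What is at stake is the interpretation of an exploratory objective, the incidence and severity of ISRs. Protocol 4.2 gives interpretation of safety and tolerability as the reason for including placebo.

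**Working it through.** **Inputs from the documents.** Injection numbers and volumes (Protocol 6.1.1, SAP 6); 125 mg/mL; 7 active and 2 placebo per cohort in Cohorts 1 and 2, and 5 to 7 active with up to 2 placebo in Cohort 3 (Protocol 4.1.1).

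**Assumptions.** Per-injection risk p, because no ISR rate or ISR precision is stated; the same p at every site in every group; placebo given by its cohort's scheme.

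**Step 1: the plan's doses reproduce.**
- Cohort 1: 2 × 1.4 = 2.8 mL; 2.8 × 125 = 350 mg.
- Cohort 2: 1.4 + 2 × 2.1 = 5.6 mL; 5.6 × 125 = 700 mg.
- Cohort 3: 2 × 1.9 + 1.8 = 5.6 mL; 5.6 × 125 = 700 mg.

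Dose is therefore fully tied to injection count between Cohorts 1 and 2. Cohorts 2 and 3 share dose, count and total volume.

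**Step 2: participant incidence, independent sites.** P(at least one ISR) = 1 − (1 − p)^m, with m injections. Pooled placebo is the average over 2 + 2 participants (Cohorts 1 and 2) or 2 + 4 (all three).

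| p | m = 2 | m = 3 | Difference (points) | Ratio | Pooled placebo |
|---|---|---|---|---|---|
| 0.10 | 19.0% | 27.1% | 8.1 | 1.43 | 23.1–24.4% |
| 0.20 | 36.0% | 48.8% | 12.8 | 1.36 | 42.4–44.5% |
| 0.30 | 51.0% | 65.7% | 14.7 | 1.29 | 58.4–60.8% |

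Example at p = 0.20: 1 − 0.8² = 0.360; 1 − 0.8³ = 0.488; (2 × 0.360 + 2 × 0.488)/4 = 0.424; (2 × 0.360 + 4 × 0.488)/6 = 0.445.

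**Step 3: what seven per group would show.** With 7 v 7 and p = 0.20, exact binomial calculation gives Cohort 2 more ISR participants than Cohort 1 with probability 0.59 and fewer with 0.22. With two injections in both groups it would be 0.39 each way.

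**Step 4: correlation within a person.** A beta-binomial model with intraclass correlation (ICC) ρ uses a = p(1 − ρ)/ρ and b = (1 − p)(1 − ρ)/ρ. The chance of no reaction in m injections is the product of (b + i)/(a + b + i) for i = 0 to m − 1. At p = 0.20:
- ICC 0: 36.0% v 48.8%, gap 12.8 points
- ICC 0.3: 31.2% v 38.6%, gap 7.4
- ICC 0.6: 26.4% v 30.1%, gap 3.7
- ICC 1: 20% v 20%, gap 0

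**Step 5: the threshold.** If participants are counted, the three-subject trigger inherits the same effect. Among 7 active participants with independent sites, the chance of reaching three is 49% with two injections and 75% with three at p = 0.20 (13% and 29% at p = 0.10).

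**Step 6: Cohort 2 against Cohort 3.** With m = 3 in both, the count artefact is zero. The comparison is imprecise all the same: assuming participant incidences of 20% and 70%, a two-sided Fisher test at 0.10 with 7 v 7 would have about 34% power.

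**The case against.** **A regimen view is legitimate.** SAP 6 names each treatment as a dose plus an injection scheme. The chance that someone given that regimen has a reaction is a fair tolerability measure. This stands, and is why the participant-level table should be kept. It does not make that table informative about dose.

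**The counting unit and the placebo scheme are not stated.** SAP 9.4.7 does not say that participants are counted, and SAP 3 leaves table layouts to a separate shell document that is not available here. That placebo follows its cohort's scheme is plausible under the blind but is an inference, and every pooled-placebo figure rests on it. Both points stand, so the finding is conditional.

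**The size is an upper case.** Independence between sites gives the largest gap. At p = 0.20 it is 0.128 × 7, or about 0.9 of a participant; at ICC 0.3 it is 0.074 × 7, or about 0.5. This stands.

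**The stakes are limited.** ISRs are exploratory and no safety inference is planned (SAP 9.4.11). The remark in Protocol 4.1.2 that ISRs are the main expected concern belongs to the sentinel decision in Cohort 1, where only the two-injection scheme applies. Escalation rests on review of all available data (Protocol 6.6.1), not on this table. This also stands.

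**Readings that go too far.** Because Protocol 4.1.2 describes the optional cohort as "Cohort 3 (optional): 700 mg (alternative injection volumes", a reader might infer that the plan cannot answer the volume question. The documents do not support that: SAP 6 lists Cohorts 2 and 3 as separate treatments labelled with their volumes, and SAP 9.4.7 tabulates by treatment. Nor does the by-dose wording of Protocol 9.4.4 settle it, since it is permissive and the SAP supersedes it. A reader might also infer that the per-injection data go unused; they will be listed, and only a stated summary is missing.

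**Conclusion.** The point holds in a limited form. Dose and injection count are tied between Cohort 1 and Cohort 2, and the SAP does not say what its ISR table counts. If it counts participants, incidence can differ by about 8 to 15 points (p from 0.10 to 0.30, independent sites) with no difference in risk per injection; the gap shrinks to zero as within-person correlation rises to 1. If placebo matches its cohort's scheme, pooled placebo falls between the two.

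The Cohort 2 v Cohort 3 comparison is free of this artefact and is preserved by the by-treatment table. It is at risk only through the per-dose threshold in SAP 9.4.7, which conflicts with the preceding sentence and needs reconciling.

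This is a low-cost improvement to a descriptive, exploratory summary. It affects neither the primary PK analysis nor the dose-escalation process.

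**What to change.** In SAP 9.4.7:

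- State the counting unit, and keep the participant-level table by treatment.
- Add a per-injection table: injections with each reaction over injections given, by treatment and injection volume (1.4 mL, 1.8 and 1.9 mL together, 2.1 mL). Protocol 10.8 shows that the 1.8/1.9 split is only syringe rounding. With 7 active per cohort the denominators are 7 × 2 = 14 at 1.4 mL in Cohort 1; 7 × 1 = 7 at 1.4 mL and 7 × 2 = 14 at 2.1 mL in Cohort 2; and 15 to 21 in Cohort 3 (5 to 7 participants × 3). The two 1.4 mL rows compare sites with the same volume and the same 175 mg, and Cohort 2 allows 1.4 v 2.1 mL within a person.
- Show placebo by number of injections as well as pooled.
- Replace *per dose* with *per treatment* in the threshold, and make clear whether the summary is planned or conditional.

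No protocol amendment is needed, because the SAP supersedes Protocol 9.4.4.

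**Cost.** SAP wording and one descriptive table from data already collected per injection. Placebo subgroups will hold about 2 to 4 participants. Injections within a person are not independent, so the rates are descriptive only. A per-injection rate removes only the injection-count effect: total volume (2.8 v 5.6 mL) and volume per site still differ with dose.
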